ClinicalTrials.gov Document Upload

DOCUMENT DATE (IRB APPROVAL):

23-Feb-2021

NCT NUMBER:

NCT03252522

OFFICIAL STUDY TITLE:

Micronutrients for ADHD in Youth:
The "MADDY" study

INVESTIGATOR NAME:

[name]

ORGANIZATION:

Oregon Health & Science University

Child RCT Protocol 2017

**Protocol for
Micronutrients for ADHD in Youth:
The “MADDY” study
at
Oregon Health & Science University
The Ohio State University/Nationwide Children’s Hospital
University of Lethbridge**

Child RCT Protocol 2017

Aims and Objectives

Aim 1: Replicate acceptability/tolerability of a multi-ingredient micronutrient product for children with ADHD [1].

Hypothesis 1: Consumption of 9-12 capsules, in 3 divided doses daily, of a product containing a blend of vitamins, minerals, amino acids and antioxidants (see Appendix A for ingredients), will be achieved at >80% success, as measured by self-report adherence and pill counts and with no or transient side effects (e.g. nausea, loose stool); and no directly attributable serious adverse events (AEs) (see definition of AE in the section on page 21) recorded via the Pediatric Adverse Events Rating Scale (PAERS).

Aim 2: Determine the prevalence, severity, and effect size for symptoms of irritability and negative mood, which are often associated with ADHD.

Hypothesis 2: Treatment will improve mood, irritability and aggression by a medium effect ($d \geq .50$) [2] as measured by the parent-rated Child & Adolescent Symptom Inventory – 5 (CASI-5), Categories B, C, CD, K, L, Rz, Q, and the child-rated Patient Reported Outcomes Measurement Information System (PROMIS) measures: Depression, Anger, Anxiety, and Peer Relations.

Aim 3: Estimate true effect sizes on ADHD symptoms in this age group, to inform a larger trial.

Hypothesis 3: The micronutrients will reduce participants' ADHD symptoms of inattention and/or hyperactivity/impulsivity, as measured by the parent-rated CASI-5, Question Category A, and the Clinician-rated Clinical Global Impression (CGI) by a medium effect ($d \geq .50$) compared to the placebo [1].

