The design is an 8-week randomized, double-blind, placebo-controlled trial, with an 8-week open-label extension, of Daily Essential Nutrients (DEN; Hardy Nutritionals), and a 30-, 60-, and 365-day follow-up phone call or in person-visit. The follow-up calls will also assess for safety following study completion. Parent/guardian and child ratings, using standardized measures, will evaluate adherence, side effects and AEs (Aim 1); ADHD-associated mood and irritability (Aim 2); and ADHD symptoms (Aim 3), thus allowing evaluation for clinical significance. Other domains of psychopathology will be evaluated for purposes of sample characterization and secondary analyses. The design consists of three study periods, which are individualized for each participant as they enroll:

Child RCT Protocol 2017

1. Screening and baseline. Participants will be screened by phone through a conversation with the parent/guardian for study eligibility. Those who are eligible and consent/assent to the study will receive a baseline assessment (see below for definition of eligibility and assessment).
2. An 8-week period of fully randomized, placebo-controlled, treatment.
3. An 8-week open-label extension period (OL).

Study data collection will occur in-person at baseline and at weeks 4, 8, 12, and 16 and via phone 30-60- days after end-of-open label and 365- days after enrollment. Details of data collection are outlined in Tables 1 & 2 located on the last two pages of this proposal.

Study Population

Number of subjects

Sample size power calculations are based on using power = 0.8, with a two-tailed $\alpha=0.05$, and the a priori decision to detect a medium effect size ($d \geq .5$) with a primary parent-rated measure that is a combination of CASI-5 subscale scores. Given the three sites and two treatments; a 3:2 randomization ratio, active-to-placebo; and assuming two dropouts per arm, per site, based on a previous study (Rucklidge, 2017), ($n = 12$ total), sample needed to recruit = at least 135, with at least 123 retained. To account for the 3 sites and the 3:2 randomization, a number divisible by 15 is needed, so, $n = 45$ participants per site.

In terms of feasibility, we estimate being able to recruit the required number of participants over a period of 12-18 months, given proven success in recruitment for a vitamin D supplementation trial ([name]) and established success recruiting participants in a longitudinal study on ADHD ([name]).

Inclusion Criteria

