The Child & Adolescent Symptom Inventory-5 (CASI-5) will be used as a baseline screening and diagnostic tool. The CASI-5 is a behavior rating scale for DSM-5-defined emotional and behavioral disorders in youths between 5 and 18 years old. Subscales of the parent-version will be used. When the parent/guardian endorses a symptom question, s/he will be asked for an example, when a symptom question is answered "often" or "very often" and also asked for additional detail about the setting or settings in which the behavior occurs. Each symptom category includes an Impairment question (i.e., the degree to which symptoms interfere with the youth's social or academic functioning). Subscales to be used at baseline, end-of-RCT and end-of-Open Label are questions from: Categories A, B, C, Cz, D, E, G, I, Rz, K, L, M, Q. These include questions about ADHD, Disruptive Mood Dysregulation Disorder (DMDD), anxiety, depression, Obsessive Compulsive Disorder (OCD)/Post Traumatic Stress Disorder (PTSD), tics, mania, psychosis, separation anxiety, Autism Spectrum Disorders (ASD) (which is an exclusion), enuresis/encopresis, and Oppositional Defiant Disorder (ODD).

Demographics

Demographic information will also be collected including ethnicity, parent/guardians' occupation, parent/guardians' level of education, and family income so that Socioeconomic Status (SES) can be estimated.

Study personnel-rated measures

Completed at baseline and at assessments every 4 weeks – time: 30 minutes:

1. **Vital Signs and Body mass index-BMI** - height and weight plus pulse and blood pressure, adverse events, will be assessed at every in-person visit. BMI will be calculated using the standard formula from the participant's height and weight, as measured with a scale and stadiometer. Blood pressure and pulse will be measured using standardized hospital equipment.
2. **Adverse events** will be measured using the Pediatric Adverse Event Rating Scale (PAERS), and the Columbia Suicide Severity Rating Scale (CSSRS) with questions asked of the

Child RCT Protocol 2017

parent/guardian and participant. Both of these measures were requested by the Federal Drug Administration upon review of an IND application by [name] for a similar proposed study, specifically to standardize reports.

3. **Pill count compliance** will be monitored by the assessor at in-person visits by counting the remaining pills.
Completed at end of week 8:

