Our primary outcome measures defined *a priori*, reflecting the often co-morbid ADHD symptoms of irritable mood and aggression are the CASI-5 subscales and the clinician CGI. The changes from baseline to the end of treatment will be compared between randomized groups using repeated-measures ANCOVA, with the baseline level as the covariate. The differences between treatment groups in these measures will be summarized as the mean differences and 95% confidence intervals generated from the ANCOVA/ANOVA models. Categorical outcomes will be compared between groups using Chi-square tests and will be described using odds ratios and 95% confidence intervals. All analyses will be undertaken on an intention-to-treat (ITT) basis that includes all randomized participants analyzed according to the group to which they were randomized. For those participants not completing the 8 weeks, data from their final assessment (last observation carried forward) will be used to evaluate the change scores. Secondary analyses will be undertaken on all outcomes using the per-protocol (completers) analysis set. All tests will be two tailed and any *p* values less than 0.05 will be considered statistically significant.

Privacy, Confidentiality, and Data Security

All staff involved in the conduct and/or monitoring of this study will have completed the requisite Human Subject Protection Training for each IRB. Documentation of training will be held in locked cabinets or secure password protected computers at each site. Prior to implementation of any protocol changes, amendments will be submitted to the Institutional Review Boards for approval. The site PIs will be responsible for continuous data and safety monitoring of all participants enrolled in this study at their respective sites; discussion of any data or safety monitoring concerns will be routinely brought up as part of weekly study coordination meetings across sites. Overt identifying information will be separated from collected data and specimens.

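### The trial is sized on one parent-rated CASI-5 combination, but Data Analysis names the CASI-5 subscales and the CGI as primaries, each tested at 0.05 with no success rule

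*Combined protocol and SAP*

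**What the plan says.** **Number of subjects (Study Population).** The calculation uses power 0.8, two-tailed alpha 0.05 and d of at least 0.5, "with a primary parent-rated measure that is a combination of CASI-5 subscale scores". Allocation is 3:2 and the result is "sample needed to recruit = at least 135, with at least 123 retained".

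**Data Analysis.** The primaries are plural and declared a priori. They are said to reflect "ADHD symptoms of irritable mood and aggression are the CASI-5 subscales and the clinician CGI". The combination used for sizing does not appear. Continuous outcomes go to repeated-measures ANCOVA with baseline as covariate, and categorical outcomes to chi-square tests. The main set is all randomised children, with last observation carried forward. The only decision rule is that any p "values less than 0.05 will be considered statistically significant".

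**Aims and Objectives.** Hypothesis 2 lists CASI-5 "Categories B, C, CD, K, L, Rz, Q" for mood, irritability and aggression. Hypothesis 3 places the CGI with ADHD Category A and expects a medium effect on it. Neither hypothesis calls any measure primary.

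No section of the document as supplied lists the categories or scoring of the combination, orders the primaries, adjusts for their number, or says whether one or all must succeed.

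**The concern.** The stated alpha and power describe one test of one measure, and the analysis section does not say that this test decides the trial. If the combination and the CGI disagree at week 8, the plan neither permits nor forbids a positive primary claim on one alone.

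The primaries are also not fully specified. The combination cannot be computed from the document. Teachers or other adults complete CASI-5 subscales too, and Data Analysis does not repeat that the primary is parent-rated. It is not stated which CGI score is primary: the dosing section uses CGI-Improvement, while the clinician measures section describes a single-item severity rating. Nor is it stated whether the CGI goes to ANCOVA or chi-square. Choices left open until the data are seen cannot be pre-specified afterwards.

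**Working it through.** **Inputs from the document:** d = 0.5, two-sided alpha 0.05, power 0.80, 3:2 allocation, 135 randomised (81:54). **Assumptions:** correlation between the two test statistics of 0 to 0.8; d = 0.5 on both; CGI treated as continuous. Normal approximation throughout.

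**1. The plan's own figure.** With ratio k = 1.5, total N = [(1+k)²/k] × (1.960 + 0.842)²/d² = 4.167 × 7.849/0.25 = 130.8. Rounded up by arm this is 53 + 80 = 133, which agrees with 135 if all are analysed. The expected test statistic is 0.5 × √(81×54/135) = 2.846, so power for one test is Φ(2.846 − 1.960) = 0.812. The sizing therefore matches one primary at an undivided 0.05.

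**2. Narrowest reading: combination plus CGI, either may win.** With independent tests the chance of at least one false positive is 1 − 0.95² = 0.0975. Integrating the bivariate normal for correlated tests gives:

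| Correlation | False-positive chance |
|---|---|
| 0 | 9.8% |
| 0.5 | 9.1% |
| 0.8 | 7.8% |

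Testing several mood and irritability subscales singly would raise this further.

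**3. Same reading, both must win.** Type I error stays at or below 5%. Power without covariate gain is 0.8122² = 0.660 at correlation 0, 0.704 at 0.5 and 0.744 at 0.8.

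**4. Effect of the baseline covariate on step 3.** ANCOVA with baseline correlation r gives an effective d of 0.5/√(1 − r²).
- r = 0.3: d = 0.524, statistic 2.983, power per test 0.847. Joint power is 0.847² = 0.717 at correlation 0 and 0.787 at 0.8, still under 80%.
- r = 0.5: d = 0.577, statistic 3.286, power per test 0.908. Joint power is 0.908² = 0.824 even with independent tests.

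**5. Keeping both primaries with error control.** At 0.025 the critical value is 2.241 and power per test is Φ(2.846 − 2.241) = 0.727.
- At least one succeeds: 1 − (1 − 0.727)² ≈ 0.926 at correlation 0, and 0.812 at 0.8.
- Holm, for a given endpoint: 0.727 + (0.812 − 0.727) × 0.727 ≈ 0.789 at correlation 0, and 0.770 at 0.8.

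**The case against.** **The sections can be reconciled.** The sizing text speaks of a parent-rated primary and Data Analysis adds a clinician-rated one. With the subscales as shorthand for the combination, there is one primary per rater. This is a fair reading, and the figures above use it. It still leaves two primaries, because a parent-rated combination cannot contain a clinician rating, and still no success rule.

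**The trial is partly an estimation exercise.** Aim 3 is to estimate effects for a larger trial, and Data Analysis reports mean differences with 95% intervals. This lowers the stakes. It does not settle the matter, because a declared primary is powered and tested at 0.05.

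**Stronger readings that the document does not support.**
- A reader might infer that every collected subscale ("Categories A, B, C, Cz, D, E, G, I, Rz, K, L, M, Q") is primary, giving 14 tests with the CGI. That list says what is administered, and Data Analysis ties its primaries to irritable mood and aggression. The Hypothesis 2 list is not labelled primary either, so no error rate should be quoted for either set.
- A reader might infer that two primaries require a larger trial, since power per endpoint at 0.025 is only 73%. If either primary suffices, what counts is the chance that at least one succeeds. That is 81% to 93%, against 81% for a single primary.
- A reader might infer that requiring both must leave the trial underpowered. That holds without covariate gain, but not necessarily with a strong baseline covariate.

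**Conclusion.** The concern holds and should be fixed before unblinding. As written, the significance rule applied to the declared primaries does not preserve the 5% level used for sizing, unless both are required to succeed, which the plan does not say. If either may win, the false-positive chance for a primary claim is 7.8% to 9.8%. If both must win, power is about 66% to 74% at 135 before any covariate gain, below the stated 80%. These figures rest on the assumed correlation range and a continuous CGI; the power figures also rest on d = 0.5 for both measures. The sample size itself is consistent with a single primary and is not in question here.

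**What to change.** **Preferred.** Amend Data Analysis before unblinding:
- Name the parent-rated CASI-5 combination as the single primary at two-sided 0.05, tested by the planned baseline-adjusted ANCOVA, with its categories and scoring listed.
- Make the CGI the key secondary, tested only if the primary is significant. State which CGI score is used and whether it is continuous or categorical.
- Report individual subscales as secondary, either Holm-adjusted or as estimates with confidence intervals.

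N and alpha do not change. The costs are that the CGI loses its declared primary status, a lone CGI or subscale result could no longer be called a positive primary, and each site's IRB must approve the amendment.

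**Alternative, if the sponsor keeps both as primary.** State either Holm (one suffices) or both required at 0.05, define both measures as above, and restate power. Under Holm, power for a given endpoint at 135 is about 77% to 79% without covariate gain, and the chance that at least one succeeds is about 81% to 93%, so no increase in N is needed. If both are required, the restated power should give the baseline correlation that it relies on.

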Recent research highlights the importance of considering nutritional factors in the expression of ADHD, based on investigations into the impact that processed foods play in symptom severity[17], the roles of food dyes[18] and essential fatty acids[19], and long-term studies showing that early malnutrition is an important risk factor for ADHD[20]. One treatment that logically stems from these studies is providing individuals with ADHD with the nutrients required for optimal brain functioning. One method to achieve this would be through supplementation with micronutrients (vitamins and minerals), based on the assumption that micronutrients serve as cofactors for synthesizing essential neurotransmitters. Such an approach may seem to challenge conventional understanding that only one variable at a time should be manipulated. However, a single ingredient strategy is already known to be of limited utility and also is at odds with human physiology as optimal functioning requires presence of all nutrients in balance rather than one nutrient provided in high doses[21]. Indeed, single nutrient studies have yielded only modest findings[22] whereas research with multi-ingredient nutrient interventions are proving more promising[23-27]. Pilot research has demonstrated on-off-on-off control of symptoms in ADHD children using micronutrients and a just-published RCT in children in New Zealand has shown clinical symptom improvement, particularly in children with comorbid irritability, aggression and anger [4]. These results all point to the need for a controlled trial with children, run in the US, as well as trials that investigate mechanisms of action of the micronutrients to document the transformational potential of nutritional therapy for ADHD.

Rationale and approach of RCT

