Once parent/guardian has signed consent and child participant has signed assent, and following the completion of baseline questionnaires and recording of vitals, including blood pressure, pulse, height and weight, the participant will be considered to be enrolled in the study. Enrollment may be delayed until any questions that may have arisen during the baseline assessment are discussed with and answered by the study physician. Once enrolled, the participant will be randomized to a treatment, either active or placebo, and a notification of participation letter will be sent to the child's primary care physician with the parent/guardian signature on the release of information form. Parent/guardian will be given study capsules for the initial 4 weeks as noted below.

Randomization

The randomization scheme will be generated for all three sites, as a whole, by the study statistician at OHSU using REDCap, with the randomization sequence arranged in permuted blocks of size 5, in a 3 active to 2 placebo ratio. The randomization scheme will be emailed to the other two sites. Neither the participants nor the clinicians involved in the study will have access to the randomization until end of study, but access will be available to the medical oversight person at each site and Data Safety Monitoring Board members in event of emergency. A pharmacist or designated unblinded research team member at each site will prepare individual participant pill kits in advance, per the randomization scheme. The pill kits include 1-week pill caddy containing the capsules to be taken during the first week (titrated up to the full dose by Day 5), from pre-labeled and packaged bottles sent from the manufacturer. The pill caddy, together with the bottle of pills for the rest of the month will be individually labeled and put inside a white paper bag to be given to each participant. These kits will be sequentially numbered and allocated to placebo or micronutrients based on the randomization list. The pharmacy research staff at OHSU, who is unblinded, will be available 24/7

Child RCT Protocol 2017

as per on-call schedule, to break the blind for an individual subject if medically necessary. Each participating family will be given the appropriate local clinician name and contact information in the case of a side effect or question or urgent notification for any medical emergencies.

Micronutrient formula, titration and dosing

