The study will be using a product called Daily Essential Nutrients (DEN) from Hardy Nutritionals, which consists of a blend of vitamins, minerals, amino acids and antioxidants; see Appendix A for ingredients of both DEN and placebo, beginning on page 27. Participants will be given one pill caddies with 7-day sections divided into 3x/day dosing that contain the pills for the first week of the study and will receive instructions on how to store the caddie at home. The remaining pills will be in a labeled bottle with the participant's name. Participants will be asked to take one capsule, 3 times each day, with plenty of food and water, and asked to increase the dose by three capsules every two days, up to 9 capsules per day, in 3 divided doses, for the first four weeks. For 6-8 year olds, this will represent the maximum dose; for 9-12 years old, up to 12 capsules per day is the maximum. At week one, research staff will check in with each participant's parent/guardian via phone to see how the participant is responding and answer any questions. At this call and during any subsequent contact (other phone calls, week-4 study visit), any decision to increase dose up to a maximum of 12 capsules for participants ages 9-12 will be made in consultation with the site PI, and will depend on parent/guardian/participant report of side effects, if any; participant's ability to swallow the capsules; and parent/guardian/participant report of symptom profile, noting whether any improvement or worsening has occurred. Symptom questions from the CASI-5 eligibility questions will be used to ascertain any symptom change. These data will inform the site PI- or designate-rated CGI-Improvement scale to determine if dose needs to be increased to 12 capsules/day, based on a score of 3 or more on the CGI, for participants who are 9-12 years old. Dose can be lowered from 9 or 12 at any time for concerns regarding any AEs, as clinically determined by the site PI or their designate. Designates will be physicians or PhD-level licensed psychologists with clinical experience using micronutrients. At the return visit, participants will return the pill caddie and any remaining pills to receive the bottle of pills for the next month. The participant's parent will be responsible for filling the pill caddie with a reminder from study staff.

Adherence

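### With 3:2 allocation, the default ANCOVA intervals are calibrated only if both arms have equal residual spread; the plan should name a variance estimator that does not need this (minor)

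*Combined protocol and SAP*

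**What the plan says.** Under Data Analysis, changes from baseline to end of treatment "will be compared between randomized groups using repeated-measures ANCOVA, with the baseline level as the covariate". Results are summarised as "the mean differences and 95% confidence intervals generated from the ANCOVA/ANOVA models". Tests are two-sided at 0.05, and the main analysis keeps every randomized child in the assigned arm, carrying the last observation forward.

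Under Randomization, the sequence is in "permuted blocks of size 5, in a 3 active to 2 placebo ratio". Number of subjects gives the target as "at least 135, with at least 123 retained".

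The document does not mention a robust standard error, a residual variance for each arm, a Welch-type comparison or a check of equal variances, and it gives no SD by arm.

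**The concern.** An ordinary ANCOVA estimates one residual variance and applies it to both arms; the usual repeated-measures default is likewise one covariance matrix shared by the arms. With equal arms, a difference in spread cancels out of the standard error of the treatment contrast. With unequal arms it does not, because the larger arm dominates the pooled variance while the smaller arm contributes more to the true variance of the contrast.

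Two features of the trial could make the active arm more variable. The Background reports that benefit in an earlier trial was greater in children with accompanying irritability, aggression and anger. The dosing section also lets the capsule count differ between children ("any decision to increase dose up to a maximum of 12 capsules for participants ages 9-12" is decided child by child), and actual exposure to the product then differs only in the active arm.

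At stake are the calibration of the p-values and 95% intervals for outcomes analysed by these models and, if the active arm is the more variable, a little power.

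**Working it through.** **Arm sizes.** 135 × 3/5 = 81 active and 135 × 2/5 = 54 placebo. Two dropouts per arm at each of three sites is 12, and 135 − 12 = 123, split 75:48.

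**The plan's own figure.** For d = 0.5, two-sided alpha 0.05, power 0.80 and 3:2 allocation, the placebo arm needs (1 + 1/1.5) × ((1.960 + 0.842)/0.5)² = 52.3, so 53, with 80 active: 133 evaluable. That is close to the 135 recruited (power 81.2% at 81:54). It does not match 123 retained, where power at 75:48 is 77.2% without credit for baseline adjustment. That gap is a separate matter; here it shows only that there is little power to spare.

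**Formulas.** Let s1 and s0 be the residual SDs in the active and placebo arms.
- True variance of the contrast: s1²/81 + s0²/54.
- Default (pooled) variance: [(81·s1² + 54·s0²)/135] × (1/81 + 1/54).
- q = √(default/true). True alpha = 2[1 − Φ(1.96q)]. Power, where a correct standard error would give 80%: Φ(2.802 − 1.96q).

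**Example, s1/s0 = 1.5.** True: 2.25/81 + 1/54 = 0.04630. Default: (236.25/135) × 0.03086 = 0.05401. So q = √(0.05401/0.04630) = 1.080 and alpha = 0.034.

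**Results at 81:54.** The SD ratios are assumptions.

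| More variable arm | SD ratio | q | True alpha | Power (correct SE: 0.80) |
|---|---|---|---|---|
| Active | 1.12 | 1.022 | 0.045 | 0.787 |
| Active | 1.2 | 1.037 | 0.042 | 0.78 |
| Active | 1.3 | 1.053 | 0.039 | 0.77 |
| Active | 1.5 | 1.080 | 0.034 | 0.75 |
| Placebo | 1.2 | 0.965 | 0.059 | – |
| Placebo | 1.3 | 0.950 | 0.063 | – |
| Placebo | 1.5 | 0.926 | 0.070 | – |

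**Where 1.12 comes from.** Take the placebo residual SD as 1. Suppose half the active children gain one SD and half gain nothing, so the mean effect is the targeted 0.5. The variance of the effect is 0.5 × 0.5 × 1² = 0.25, and the SD ratio is √1.25 = 1.12. If individual effects are independent of the outcome on placebo, ratios of 1.3 and 1.5 need effect SDs of √(1.69 − 1) = 0.83 and √(2.25 − 1) = 1.12.

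**Simulation.** With an assumed baseline–outcome correlation of 0.5, 40,000 trials per setting at 81:54 and active/placebo ratios from 0.5 to 2, alpha ran from 0.083 to 0.027 with the default standard error and stayed at 0.046 to 0.050 with HC3. At 67:67 the default test stayed at 0.049 to 0.053, so the error comes from the unequal allocation. In a separate run of 8,000 trials per setting, with the active arm more variable by 1.2, 1.3 and 1.5, power was 0.775, 0.759 and 0.750 by default and 0.788, 0.783 and 0.791 with HC3: gains of 1.3, 2.4 and 4.1 percentage points.

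**Completers analysis.** At 75:48 and a ratio of 1.5, alpha is 0.033 (active more variable) or 0.072 (placebo more variable).

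**The case against.** The strongest case against is that the arithmetic is right but matters little here.

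- Inclusion criterion 4 requires every child to show some irritability or anger. The trial therefore enrols mostly the kind of child who responded in the earlier study, which removes much of the expected contrast between responders and non-responders. This stands.
- The dose increase is prompted by poor response, applies only to ages 9-12 and is added to a common 9-capsule level. It could narrow or widen the spread, and the documents do not say which. This stands too, so neither ground for unequal spread is strong.
- Ratios of 1.3 to 1.5 are large for an effect of 0.5. The responder mix above gives 1.12, where the standard error is off by only 2%.
- Comparing 0.75 with 0.80 overstates what the fix recovers, because HC3 itself reached 0.78 to 0.79 in simulation.

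A reader might infer that the primary test exceeds its 0.05 level. The documents do not support that. It needs a more variable placebo arm, for which they give no reason. If the product changed no child's outcome, the arms would have the same spread and the test would be calibrated.

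A reader might also infer that the plan commits to a pooled variance, or that every primary measure is affected. The plan leaves the estimator unnamed, and the common variance is only the usual default. The clinician CGI is also named as primary, categorical outcomes go to chi-square tests, and the plan does not say how the CGI will be classed.

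What survives is that the stated coverage depends on an equal-spread assumption that the plan neither states nor checks.

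**Conclusion.** The point holds as a minor one. Under the default reading of the named models, the p-values and 95% intervals at 81:54 are calibrated only if residual spread is equal between arms. The better-supported direction is conservative: standard errors about 2% too wide at a ratio of 1.12 and 4% to 8% at 1.2 to 1.5, with alpha between about 0.045 and 0.034. Over ratios of 1.2 to 1.5, robust standard errors recover about 1 to 4 points of power. The liberal direction, with alpha of about 0.059 to 0.070 at ratios of 1.2 to 1.5, is possible in principle but has no support in the documents.

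These sizes rest on assumed SD ratios and on the plan using the default variance. It is worth settling in advance because the direction of any error is unknown, and choosing the standard error after seeing the arm variances would be a data-dependent choice.

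**What to change.** In Data Analysis, keep the baseline-adjusted model and its point estimate, and add one sentence: for outcomes analysed as continuous, the p-value and 95% confidence interval for the end-of-treatment contrast use HC3 heteroscedasticity-robust standard errors or, if a mixed repeated-measures model is fitted, a separate residual covariance matrix for each arm.

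This takes one sentence and one software option, with no new data, visits or participants. The downside is an interval about 1% wider if the arms truly have equal variance.
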